### 3. List of Abbreviations and Definition of Terms

AE	Adverse Event
ARR	Annualized Relapse Rate
CI	Confidence Interval
CRF	Case Report Form
EDSS	Expanded Disability Status Scale
HCP	Health Care Professional
ICF	Informed Consent Form
IFN $\beta$	Interferon beta
MedDRA	Medical Dictionary for Regulatory Activities
MS	Multiple Sclerosis
MusiQoL	Multiple Sclerosis International Quality of Life Questionnaire
PT	Preferred Term
RRMS	Relapsing Remitting Multiple Sclerosis
SAE	Serious Adverse Event
SAP	Statistical Analysis Plan
SAS	Statistical Analysis System
SOC	System Organ Class
TSQM v II	Treatment Satisfaction Questionnaire for Medication Version II

**4. Modification History**

Unique Identifier for SAP Version	Date of SAP Version	Author	Changes from the Previous Version
0.1	21OCT2016	PPD [REDACTED]	Baseline Version
0.2	03NOV2016	PPD [REDACTED]	Based on client comments
0.2	24FEB2017	PPD [REDACTED]	Based on client comments
0.2	08MAR2017	PPD [REDACTED]	Based on client comments
1.0	12MAY2017	PPD [REDACTED]	Final Version

## **5. Purpose of the Statistical Analysis Plan**

The purpose of this Statistical Analysis Plan (SAP) is to document technical and detailed specifications for the final analysis of data collected for protocol EMR200136\_597. Results of the analyses described in this SAP will be included in the Clinical Trial Report (CTR). Any post-hoc, or unplanned analyses performed to provide results for inclusion in the CTR but not identified in this prospective SAP will be clearly identified in the CTR.

The SAP is based upon trial protocol and is prepared in compliance with International Council for Harmonization of Technical Requirements for Pharmaceuticals for Human Use (ICH) E9 Guidelines. The SAP focused on measuring satisfaction of treatment with Rebif after discontinuing initial treatment of MS using TSQM v II. Statistical analyses for other variables such as Annualized Relapse Rate, Adherence, MusiQoL Questionnaire and Safety (frequency and severity of AEs) are also added in this version of SAP.

**6. Summary of Clinical Trial Features**

Study Title
	
A Phase IV, prospective, multicenter, open label, uncontrolled, non-interventional, single arm study to measure treatment satisfaction of multiple sclerosis (MS) patients on Rebif® after discontinuing initial first-line treatment

Study acronym/Short title
	
MESTRE-MS (MEasuring Satisfaction of Treatment with REbif after initial treatment of MS)

Study Protocol Date / Version
	
07OCT2016 / Version 2.0

Study Rationale and background
	
The purpose of this study is to investigate treatment satisfaction in MS patients, who have discontinued first-line MS oral or injectable MS medication, and have initiated treatment with Rebif. MS patients who are starting their first treatment for MS currently can be treated with various oral or injectable medications. When solely considering the route of administration of these medications it may appear that the oral treatments are more patient friendly and convenient than the injectable ones. In addition, certain weekly or daily first-line injection treatments may be preferred over thrice weekly injections for unknown reasons. In clinical trials, discontinuation rates due to adverse events of dimethyl fumarate (Tecfidera®) and of teriflunomide (Aubagio®) treated patients is 16% in both DEFINE and TENERE studies, respectively. Furthermore, injectable treatment discontinuation varies between 14% and 47%. It is important for patients to optimally utilize first-line MS

	
treatment options before escalating therapy to more potentially dangerous second line therapies such as natalizumab, fingolimod or alemtuzumab.
 
This Phase IV clinical study is being proposed to support decision making for health care professionals (HCPs) and patients who have decided to initiate MS treatment, and use arguments of patient friendliness and convenience for their decision. Therefore, in this study treatment satisfaction of Rebif is measured in MS patients who have discontinued their initial MS treatment, and who have decided to start Rebif as their Follow-up treatment. Currently there is no information describing the experiences with discontinuation of oral or injectable medication and the initiation of the injectable therapy Rebif. This information is crucial for HCPs and patients to be able to make a well informed decision on what to expect of their treatment. In this study, by measuring treatment satisfaction before and after Rebif treatment we aim to evaluate the difference in treatment satisfaction (as perceived by the patient), reasons to stop initial treatment, and experience after alternative treatment initiation.
 
This study will add the additional data on the perception of treatment convenience and reasons for discontinuation of oral or injectable first-line treatment.

Study objectives	Primary objective 

• To determine the level of treatment satisfaction as measured with the Treatment Satisfaction Questionnaire

	
for Medication Version II (TSQM v II), in relapsing remitting MS (RRMS) patients who have discontinued their initial oral or injectable MS treatment, and have initiated treatment with Rebif.
 
Secondary objectives
 
 
• To evaluate the change in annualized relapse rate (ARR) in patients changing from initial oral or injectable forms of treatment to Rebif
 
• To assess therapy adherence to Rebif
 
• To determine the change in quality of life with Multiple Sclerosis International Quality of Life Questionnaire (MusiQoL) between Baseline, Month 6 and Month 12
 
• To document the reasons for discontinuation of initial MS treatment
 
• To evaluate the potential correlations between the following measurements: TSQM v II, ARR, adherence, reasons for discontinuation, MusiQoL and TSQM v II subscales
 
• To assess the difference between TSQM v II subscales between Baseline, Month 6 and Month 12.
 

Variables and Study Endpoints
	
The variables that will be evaluated in this study include demographics, MS history, prior and current medication, pertinent medical history, treatment satisfaction score determined with TSQM v II, ARR, treatment adherence, quality of life determined with MusiQoL questionnaire, reasons for discontinuation of previous therapy and adverse events.
 
Primary Endpoint:
 
 
• Treatment satisfaction score determined with TSQM v II
 

	
from Baseline to Month 6 and to Month 12.
 
Secondary Endpoints:
 
 
• ARR (after 12 months of Rebif treatment)
 
• Adherence (after 6 and 12 months of Rebif treatment)
 
• MusiQoL (compare Baseline with after 6 and 12 months of Rebif treatment)
 
• Reason/s for discontinuation of initial MS treatment (oral or injectable).
 
 
Additional Secondary Endpoints:
 
 
• Correlation between TSQM v II and ARR; TSQM v II and adherence; TSQM v II and reason for discontinuation
 
• Correlation between MusiQoL and ARR; MusiQoL and adherence; MusiQoL and reason for discontinuation
 
• Correlation between TSQM v II subscales and adherence
 
• Correlation between TSQM v II subscales and reasons for discontinuation
 
• Difference between TSQM v II subscales at Baseline and after 6 and 12 months of Rebif treatment
 
• ARR before study entry compared to ARR at study end
 
• Association between ARR and treatment adherence.
 

Study Design
	
This is a prospective, multicenter, open label, uncontrolled, non-interventional, single arm study to measure treatment satisfaction of RRMS patients on Rebif after discontinuing initial first-line treatment.
 
This study consists of three visits:
 
 
• Visit 1: Baseline
 

	
 
• Visit 2: Month 6
 
• Visit 3: Month 12
 
 
This study will enroll RRMS patients who have discontinued their oral or injectable first-line MS medication and have decided to initiate subcutaneous Interferon beta-1a (IFN <math>\beta</math> -1a) (Rebif) treatment before Baseline measurements. MusiQoL and TSQM v II will be measured at Baseline, Month 6 and Month 12. Relapses and adherence will be assessed at Month 6 and Month 12. Adherence to Rebif therapy will be collected electronically using RebiSmart 2.0.
 
Since this is a non-interventional study, there will not be any study required clinical interventions and laboratory assessments.


Study Population and Eligibility Criteria
	
RRMS patients who have discontinued their initial MS treatment and for whom MS treatment is required according to the decision of the HCP and patient.
 
Inclusion Criteria:
 
The patient can be included when the patient
 
 
• Is male or female, 18 to 65 years of age (both inclusive), at the time of informed consent
 
• Is diagnosed with RRMS according to McDonald criteria 2010
 
• Has discontinued treatment with dimethyl fumarate (Tecfidera), teriflunomide (Aubagio), glatiramer acetate (Copaxone®), intramuscular IFN<math>\beta</math>-1a (Avonex®), pegylated interferon (Plegridy®), subcutaneous IFN<math>\beta</math>-1b (Betaferon®) or fingolimod (Gilenya®) within 6 months prior to Visit 1
 

- Is currently treated with Rebif using RebiSmart 2.0, for a maximum of 6 months prior to Visit 1
- Has a score on the Expanded Disability Status Scale (EDSS) between 0 to 5.0 inclusive
- Is willing and able to give informed consent.

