**Secondary Endpoint analysis:**

ARR and its associated 95% CI before study entry and after 12 months of Rebif treatment will be summarized overall and by previous MS therapy.

Reasons for discontinuation of previous therapy and adherence after 6 and 12 months of Rebif treatment will be summarized descriptively and overall.

Changes in MusiQoL after 6 and 12 months of Rebif treatment versus Baseline will be analysed using same methodology as for Primary Endpoint.

Additional Secondary Endpoints as correlation analysis between TSQM and MusiQoL versus ARR, adherence and reason for discontinuation will also be analyzed.

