## 16.2 Secondary Endpoint Analyses

### Annualized Relapse Rate (ARR):

The quantitative variables,

- Annualized Relapse Rate before study entry
- Number of relapses during the study
- Annualized Relapse Rate on study

will be summarized for prior MS Therapy categories and overall using descriptive statistics from Safety Analysis Set.

Annualized Relapse Rate before study entry = (No. of Relapses within 24 months prior to written informed consent / (30.4375\*24)) \* 365.25

Annualized Relapse Rate on study = (Sum of No. of Relapses at month 6 and month 12/ Time on Study) \* 365.25

where,

Time on Study (days) = (Date of Study Completion or Date of study discontinuation - Date of first Rebif administration +1)

95% Confidence Interval (CI) will also be provided for Annualized Relapse Rate before study entry and on study.

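### The change in ARR is a stated objective and endpoint, but the SAP plans no estimate or confidence interval for the within-patient change

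*SAP*

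**What the plan says.** In SAP section 6, the first secondary objective is "To evaluate the change in annualized relapse rate (ARR) in patients changing from initial oral or injectable forms of treatment to Rebif". The additional secondary endpoints in the same section include "ARR before study entry compared to ARR at study end".

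The analysis text is narrower. The synopsis paragraph on secondary endpoints states: "ARR and its associated 95% CI before study entry and after 12 months of Rebif treatment will be summarized overall and by previous MS therapy". Section 16.2 defines one rate per period for each subject:

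- before entry: "Annualized Relapse Rate before study entry = (No. of Relapses within 24 months prior to written informed consent / (30.4375\*24)) \* 365.25"
- on study: "Annualized Relapse Rate on study = (Sum of No. of Relapses at month 6 and month 12/ Time on Study) \* 365.25"

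It says these "will be summarized for prior MS Therapy categories and overall using descriptive statistics from Safety Analysis Set", and adds: "95% Confidence Interval (CI) will also be provided for Annualized Relapse Rate before study entry and on study".

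Section 16.2 later has a block for the additional secondary endpoints. Every other item on the section 6 list has an entry there; the before-versus-after ARR comparison has none. Section 9 reports no changes to the planned analyses, so the gap is not explained as a deliberate removal.

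**The concern.** The objective asks for a change, and the same patients supply both rates. The natural estimand is therefore a within-patient contrast with its own interval. The plan stops one step short, with two marginal summaries and two marginal intervals.

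This is not a uniform choice to stay descriptive. Global satisfaction (16.1), the TSQM subscales and MusiQoL (both 16.2) are all summarised as change from baseline and tested with a paired t-test. Section 11 makes every test exploratory, and that did not stop the plan from estimating those changes.

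At stake is whether the ARR objective has a pre-specified estimate with stated uncertainty. Under section 5, an analysis not identified in the SAP must be labelled post hoc or unplanned in the report. A CI for the ARR change added later would carry that label.

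**Working it through.** **1. What is planned for each change-type endpoint**

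| Endpoint | Change tabulated | Paired inference or CI of the change |
|---|---|---|
| TSQM global satisfaction (16.1) | yes | yes |
| TSQM subscales (16.2) | yes | yes |
| MusiQoL (16.2) | yes | paired t-test |
| ARR before versus on study (16.2) | no | no |

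The negative binomial or Poisson regression at the end of 16.2 does not fill the gap. Its outcome is the on-study relapse count, and prior relapses are only a candidate covariate. It gives no before/after contrast.

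**2. The plan's own formula.** Pre-entry ARR is relapses × 365.25 / (30.4375 × 24) = relapses × 365.25 / 730.5 = relapses × 0.5. Both ARRs exist per subject, so a within-patient contrast needs no new type of data.

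**3. What separate summaries can and cannot give.** For patients with both values, the mean of the differences equals the difference of the means, so the point estimate follows by subtraction. The interval does not:

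- separate half-widths: h1 = t·s1/√n and h2 = t·s2/√n
- half-width for the change: h = t·√(s1² + s2² − 2·r·s1·s2)/√n

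The within-patient correlation r appears only in h.

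**4. Illustration.** n = 106 is the evaluable number in section 7. That figure was derived for TSQM: (27.5 × (1.960 + 1.036)/8)² ≈ 106.1. The plan has no size or power figure for ARR. The SDs and r below are assumptions.

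| s1, s2 | h1, h2 | r | h for the change | h/(h1+h2) |
|---|---|---|---|---|
| 0.5, 0.7 | 0.096, 0.135 | 0 | 0.166 | 0.72 |
| 0.5, 0.7 | 0.096, 0.135 | 0.3 | 0.140 | 0.61 |
| 0.5, 0.7 | 0.096, 0.135 | 0.5 | 0.120 | 0.52 |
| 0.6, 0.6 | 0.116, 0.116 | 0 | 0.163 | 0.71 |
| 0.6, 0.6 | 0.116, 0.116 | 0.5 | 0.116 | 0.50 |
| 0.5, 0.5 | 0.096, 0.096 | 0 | 0.136 | 0.71 |
| 0.5, 0.5 | 0.096, 0.096 | 0.5 | 0.096 | 0.50 |

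The same pair of published intervals is compatible with quite different precision for the change. With both SDs at 0.6 the half-width runs from 0.163 to 0.116 as r goes from 0 to 0.5.

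**5. The windows.** On-study time starts at the first Rebif dose (16.2). The inclusion criteria in section 6 allow up to 6 months on Rebif before Visit 1. The pre-entry window runs back 24 months from consent, which the schedule of assessments places at Visit 1. The lead-in can therefore lie in both windows, taking up to 6/24 = 25% of the pre-entry one.

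Section 16.3 counts relapses since the last visit. If the Month 6 count covers only time after Visit 1, a lead-in of L months adds person-time without its relapses. One relapse in the 12 months after Visit 1 then gives:

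- L = 0: 365.25/365.25 = 1.00
- L = 3: 365.25/456.56 = 0.80
- L = 6: 365.25/547.88 = 0.67

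Under that reading the on-study rate is lowered by up to one third, and any contrast is pulled toward an apparent reduction.

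**The case against.** The strongest defence is that section 6 calls the analysis mainly descriptive, section 11 makes all tests exploratory, and the synopsis itself plans ARR as two summarised rates. Two rates side by side are a possible, if weak, reading of a comparison. This stands as a limit on weight. It does not explain why ARR alone among the change endpoints gets no change estimate.

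Four stronger readings may tempt a reader, and the document does not support them.

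- **That the objective cannot be answered at all.** Apart from missing on-study values, the mean change follows by subtraction. What is missing is its tabulation and its interval.
- **That different follow-up lengths are ignored.** Both rates are annualised per subject, the on-study one by actual time. Only weighting by precision is unaddressed: a short follow-up counts as much as a full one.
- **That the plan in effect tests at a very strict level.** Requiring two 95% CIs not to overlap, with equal standard errors, gives z = 2 × 1.96/√(2(1 − r)). That is p = 0.0056 at r = 0 and 0.0009 at r = 0.3. The arithmetic is right, but the SAP contains no overlap rule and gives neither the ratio of standard errors nor r.
- **That regression to the mean is being hidden.** It is plausible that patients who switched for lack of efficacy enter after a bad period, but the SAP does not say so. ARR by reason for stopping the earlier therapy is not a listed endpoint.

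It is also fair to object that a formal ratio on the present windows would lend precision to a biased contrast. That stands and sets the order of the fix.

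**Conclusion.** The point holds in a limited form. The change in ARR is named as an objective and as an endpoint, and the SAP plans neither a tabulated estimate nor a CI for it. Two marginal intervals cannot supply that CI because they do not reflect the within-patient correlation.

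The size cannot be fixed from the document. Under assumed SDs of 0.5 to 0.7 and correlations of 0 to 0.5 with 106 patients, the half-width for the change lies between about 0.10 and 0.17 relapses per year. That is 0.50 to 0.72 of the sum of the two separate half-widths.

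The omission affects an exploratory secondary endpoint and leaves the primary analysis untouched. It should be corrected, but it does not undermine the study. The possible bias of up to one third in the on-study rate depends on the Month 6 count starting at Visit 1, which the SAP does not state outright.

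**What to change.** **First, settle the windows in 16.2.** State start and end dates for each, make them non-overlapping, and count relapses only over the person-time in the denominator. One simple option is to start on-study time at Visit 1, with the pre-entry window ending there. The text should then say that the pre-entry window may include up to 6 months on Rebif. Ending the pre-entry window at the first Rebif dose separates the treatments more cleanly, but needs dates for the lead-in relapses.

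**Then add one within-patient contrast with a 95% CI**, overall and by prior therapy. Either form would do:

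- the mean per-subject change (on-study minus pre-entry ARR) among patients with both values; or
- a before/after rate ratio from a Poisson or negative binomial GEE, with two records per patient, period as factor, log person-time as offset and patient as cluster. This form also weights patients by their follow-up.

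Report it as an exploratory before/after change that cannot be attributed to Rebif alone.

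**Cost.** A few lines of SAP text, one model and one table, mainly on data already collected, plus the work of defining the windows. Section 6 lists seven prior therapies, so an even split of 106 patients would leave about 106/7 ≈ 15 in each; the by-therapy intervals will be wide. A display by reason for stopping the earlier therapy is optional. Its downside is small groups that may not be mutually exclusive, since the SAP allows for more than one reason.

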**Exclusion Criteria**

The patient cannot be included when the patient

- Has known planned surgical procedures at the time of the informed consent that will prevent adherence to treatment with Rebif through RebiSmart 2.0
- Is diagnosed with primary progressive, secondary progressive, or progressive relapsing MS
- Is pregnant or lactating, or planning to become pregnant
- In the opinion of the Investigator has significant renal or hepatic impairment or other significant disease (e.g., cognitive or visual impairment) that would compromise adherence and completion of the study
- Reports any reason that he/she cannot complete the 1 year study
- Has a history of hypersensitivity to natural or recombinant interferon, or any other component of the formulation
- Is contraindicated for the treatment with subcutaneous IFN $\beta$ -1a therapy as per summary of product characteristics or currently approved specific country product information
- Has any other factor that in the opinion of the Investigator would make the subject unsuitable for participation in this study

	
 
• Have significant psychiatric symptoms that, in the opinion of the Investigator, would impact patient ability to comply with treatment recommendations.
 

Study Size	133 patients diagnosed with RRMS will be enrolled (63 in the Netherlands, 40 in Switzerland and 30 in Belgium).
Sample size justification	A sample size of 106 subjects will be required to have 85% power to detect at least an 8 point difference in mean TSQM scores between Baseline and Month 6 or Month 12 measurements, with the standard deviation of 27.5 and a two sided significance level of 5%. Assuming a 20% drop out rate, approximately 133 patients will be enrolled into the study in the Netherlands, Switzerland and Belgium.
Data Analysis	
Statistical analysis will be mainly descriptive. Descriptive statistics (n, mean, standard deviation, median, first quartile [Q1], third quartile [Q3], minimum, maximum) will be provided for continuous variables. Frequencies and percentages will be presented for categorical and ordinal variables. Where appropriate, 95% confidence intervals (CIs) will be presented.
 
All analyses will be performed on subjects who received at least one dose of Rebif following enrolment in the study.
 
Primary Endpoint analysis:
 
A paired two-sided t-test of the global satisfaction score (TSQM score) will be used to test the null hypothesis that there is no difference in the global satisfaction score (TSQM score) between 6, 12 months and Baseline. The corresponding 95% two-sided CI will be presented.

**Secondary Endpoint analysis:**

ARR and its associated 95% CI before study entry and after 12 months of Rebif treatment will be summarized overall and by previous MS therapy.

Reasons for discontinuation of previous therapy and adherence after 6 and 12 months of Rebif treatment will be summarized descriptively and overall.

Changes in MusiQoL after 6 and 12 months of Rebif treatment versus Baseline will be analysed using same methodology as for Primary Endpoint.

Additional Secondary Endpoints as correlation analysis between TSQM and MusiQoL versus ARR, adherence and reason for discontinuation will also be analyzed.

### Exposure

[figure not shown]
Each patient will be observed for 12 months, during this period patients will receive Rebif 22 or 44 mcg three times per week through an electronic autoinjector device (Rebismart 2.0). The details of assessments are available in the flow chart given below.

### Schedule of Assessments

Activity	Visit 1 Baseline	Visit 2 Month 6	Visit 3 Month 12 (End of Study Visit)
Patient Informed Consent	X		
Inclusion/Exclusion Criteria	X		
Demographic information	X		
Medical History / Concomitant diseases / Prior MS medications	X		
Multiple Sclerosis History (including relapses within 2 years before study entry)	X		
MS medication related adverse events and associated concomitant medications	X		
Vital Signs	X	X	X
Physical Examination	X	X	X
Neurological Examination	X	X	X
Relapse Assessment		X	X
TSQM Version II evaluation	X	X	X
MusiQoL evaluation	X	X	X
Document reasons for discontinuation of previous MS therapy	X		
Therapy with Rebif	X	X	X
Evaluation of Adherence to Therapy		X	X
Safety Recording and Reporting		X	X

